## DOCUMENT HISTORY

Final V1.0	19-Apr-2022 – Initial version.
Final V2.0	13-May-2022 – update to multiple endpoint testing strategy for secondary endpoints to reflect amendment 2 of the protocol, clarification that Scalpdex analyses will include only subjects with scalp involvement; minor update to calculation of compliance.
Final V3.0	22-Sep-2022 – Post-database lock and post-unblinding update to SAP as per FDA to amend the primary estimand and multiple imputation procedure based on recommendations from FDA during pre-NDA meeting held 9/14/2022.

## LIST OF ABBREVIATIONS

Abbreviation	Definition
AE	adverse event
ATC	anatomical therapeutic chemical
BLQ	below limit of quantification
BMI	body mass index
CDLQI	children's dermatology life quality index
CI	confidence interval
CMH	Cochran Mantel Haenszel
COVID-19	Novel coronavirus disease
CRF	case report form
CS	clinically significant
CSR	clinical study report
DBL	database lock
DBP	diastolic blood pressure
DLT	dose limiting toxicity
DLQI	dermatology life quality index
DSMB	data safety monitoring board
DSUR	development safety update report
ECG	electrocardiogram
eCRF	electronic case report form
EDC	electronic data capture
EMA	European medicines agency
FDA	food and drug administration
GCP	good clinical practice
HR	heart rate
IB	investigator's brochure
IGA	investigator global assessment
IP	investigational product

Abbreviation	Definition
IRB	institutional review board
IRT	interactive response technology
ITT	intent-to-treat
LLOQ	lower limit of quantification
MedDRA	medical dictionary for regulatory activities
MI	multiple imputation
MTD	maximum tolerated dose
NA	not applicable
NCS	non-clinically significant
PD	protocol deviation
PHQ	patient health questionnaire
PK	Pharmacokinetic
PP	per-protocol
RR	respiratory rate or relative rate
SAE	serious adverse event
SAP	statistical analysis plan
SD	standard deviation
SE	standard error
SOC	system organ class
SOP	standard operating procedure
TEAE	treatment-emergent adverse event
TESAE	treatment-emergent serious adverse event
WHO-DD	world health organization drug dictionary
WI-NRS	worst itch – numeric rating scale

## 1. OVERVIEW

This statistical analysis plan (SAP) describes the planned analysis and reporting for Arcutis Biotherapeutics, Inc. protocol number ARQ-154-304 (A Phase 3, 8-Week, Parallel Group, Double Blind, Vehicle-Controlled Study of the Safety and Efficacy of ARQ-154 Foam 0.3% Administered QD in Subjects with Seborrheic Dermatitis), dated 05-May-2022 Amendment 2. Version 1 of the ARQ-154-SAP was approved on 19-Apr-2022 and was included as background for a Type C meeting submitted to FDA on the same date. FDA's written response to Arcutis questions was received on 3-Jun-2022. In the interim, Protocol Amendment 2 and SAP Version 2.0 (13-May-2022) were created to update the multiple testing strategy for secondary endpoints. The database was locked on 17-May-2022 and unblinded on 19-May-2022. Results have since been presented at a medical conference (Blauvelt A., et al.). On 9-Sep-2022, FDA provided the following advice in preliminary feedback prior to a pre-NDA meeting held on 14-Sep-2022.

For the primary estimand, you proposed a treatment policy strategy to handle all intercurrent events, including treatment discontinuation due to adverse event or lack of efficacy. For intercurrent events of treatment discontinuation due to adverse events or lack of efficacy, we recommend a composite strategy policy where subjects will be defined as non-responders, as we consider this to be the appropriate approach for handling such events. Your proposal to handle intercurrent events of treatment discontinuation using the treatment policy strategy can be used as part of a supportive estimand.

The purpose of this version of the SAP is to document the change to the primary estimand and related multiple imputation strategies. The revised estimand will be the focus of the Clinical Study Report and NDA. Key results based on the original estimand defined in SAP versions 1 and 2 will be provided as supplemental information for the primary and secondary endpoints covered by the multiple testing strategy.

Reference materials for this statistical plan include the protocol and the accompanying sample data collection documents. Operational aspects related to collection and timing of planned clinical assessments are not repeated in this SAP unless relevant to the planned analysis.

The structure and content of this SAP provides sufficient detail to meet the requirements identified by the Food and Drug Administration (FDA), European Medicines Agency (EMA), and International Conference on Harmonization (ICH) of Technical Requirements for Registration of Pharmaceuticals for Human Use: Guidance on Statistical Principles in Clinical Trials ([ICH 1998](#)). All work planned and reported for this SAP will follow internationally accepted guidelines, published by the American Statistical Association ([ASA 2018](#)) and the Royal Statistical Society ([RSS 2014](#)), for statistical practice.

The planned analyses identified in this SAP may be included in clinical study reports (CSRs), regulatory submissions, or future manuscripts. Also, post-hoc exploratory analyses not necessarily identified in this SAP may be performed to further examine study data. Any post-hoc or unplanned, exploratory analysis performed will be clearly identified as such in the final CSR.

The statistical plan described hereafter is an *a priori* plan. It will be approved before any unblinded inferential or descriptive analysis of data pertaining to Arcutis Biotherapeutics, Inc.'s study ARQ-154-304.

## **2. STUDY OBJECTIVES AND ENDPOINTS**

### **2.1. Study Objectives**

#### **2.1.1. Primary Objective**

The primary objective of this study is to assess the safety and efficacy of ARQ-154 foam 0.3% administered once daily (QD) vs vehicle foam for 8 weeks in subjects with seborrheic dermatitis.

### **2.2. Study Endpoints**

#### **2.2.1. Efficacy Endpoints**

##### **2.2.1.1. Primary Efficacy Endpoint**

The primary efficacy endpoint of this study is success in Investigator Global Assessment (IGA) of disease severity, defined as IGA score of 'clear' or 'almost clear' plus at least 2-point improvement at Week 8.

##### **2.2.1.2. Secondary Efficacy Endpoint(s)**

The secondary efficacy endpoints of this study include the following:

- In subjects with an average weekly Baseline Worst Itch Numeric Rating Scale (WI-NRS) pruritus score of  $\geq 4$ , achievement of at least 4-point from baseline in WI-NRS pruritus score at Week 8 ("WI-NRS Success at Week 8")
- WI-NRS Success at Week 4
- WI-NRS Success at Week 2
- IGA Success at Week 4
- IGA Success at Week 2
- Achievement of an Overall Assessment of Scaling (0-3 scale) score of 0 at Week 8
- Achievement of an Overall Assessment of Erythema (0-3 scale) score of 0 at Week 8

- Achievement of an IGA score of ‘clear’ at Week 8

### **2.2.1.3. Other Secondary Efficacy Endpoint(s)**

Other secondary efficacy endpoints of this study include the following:

- Change and percent change in Scalpdex total score from baseline at Weeks 2, 4, and 8.
- Achievement of an Overall Assessment of Erythema (0-3 scale) score of 0 at Weeks 2, and 4.
- Achievement of an Overall Assessment of Scaling (0-3 scale) score of 0 at Weeks 2, and 4.
- Change and percent change from baseline in Dermatology Life Quality Index (DLQI), Children’s DLQI (CDLQI) at Weeks 2, 4, and 8.
- Change and percent change from baseline in body surface area (BSA) affected at Weeks 2, 4, and 8.
- Change and percent change from baseline in Overall Assessment of Erythema score at Weeks 2, 4, and 8.
- Change and percent change from baseline in Overall Assessment of Scaling score at Weeks 2, 4, and 8.
- Achievement of an IGA score of ‘clear’ at Week 4.
- Achievement of an IGA score of ‘clear’ at Week 2.
- Achievement of daily WI-NRS score of 0 or 1.
- Change and percent change from average weekly baseline in WI-NRS

### **2.2.2. Safety Endpoints**

The safety endpoints of this study include the following:

- Adverse events
- Local tolerability assessments
- Clinical laboratory parameters
- Vital signs/weight
- Patient Health Questionnaire (PHQ-8)
- Modified PHQ-Adolescents (PHQ-A)
- Children’s Depression Inventory 2 (CDI-2)
- Columbia-Suicide Severity Rating Scale (C-SSRS)
- Physical examinations

- Pigmentation Assessment

### **3. OVERALL STUDY DESIGN AND PLAN**

#### **3.1. Overall Design**

This is an 8-week, parallel group, double blind, vehicle-controlled study for the treatment of subjects with seborrheic dermatitis. This study will include both male and female subjects 9 years and older having an IGA score of at least “Moderate” (3). Approximately 450 subjects will be enrolled. Subjects should not have more than 20% body surface area (BSA) of seborrheic dermatitis. After having met all inclusion criteria, and none of the exclusion criteria, subjects will be randomized in a 2:1 ratio to ARQ-154 foam 0.3% QD (Roflumilast foam 0.3%) or Vehicle foam QD on Baseline Day 0 which will be applied to areas of lesions of seborrheic dermatitis. The interval between Screening and Baseline Day 0 could be up to 4 weeks followed by 8 weeks of treatment phase. The total duration of the study is anticipated to be around 12 weeks. Subjects will have to apply the study drug once a day in the evening, except for on Day 0 and Week 2, the study drug is applied at the study site. Subjects have to record the date and time each dose has been applied, any missed doses, and any additional comments.

#### **3.2. Sample Size and Power**

A sample size of approximately 450 subjects is planned for the study. Approximately 300 subjects will receive ARQ-154 foam 0.3%; approximately 150 subjects will receive vehicle foam. This will provide at least 90% power to detect a 25% difference between treatment groups on IGA success at  $\alpha=0.01$  assuming the proportion of IGA success at vehicle arm was 40% (odds ratio of 2.79 for Roflumilast vs. vehicle). The number of subjects to be enrolled will also provide sufficient power for the secondary endpoints. Additionally, the larger study size is included in order to provide additional/sufficient number of subjects on ARQ-154 treatment for a safety database.

#### **3.3. Study Population**

Study population consists of male and female subjects of age 9 years or older with no more than 20% BSA of seborrheic dermatitis. Subjects should have a minimum IGA of ‘Moderate’ (3) at baseline.

#### **3.4. Treatments Administered**

Subjects who meet the eligibility criteria will be randomized to 1 of the 2 following treatment groups in a 2:1 ratio (active:vehicle):

- ARQ-154 foam 0.3% QD (Roflumilast foam 0.3%)
- Matching vehicle foam QD

### **3.5. Method of Assigning Subjects to Treatment Groups**

Randomization will take place at the Baseline visit after the Investigator confirms that the subject meets all eligibility criteria listed in the protocol. Subjects will be randomly assigned to apply ARQ-154 foam 0.3% QD or vehicle QD by an interactive response technology system (IRT).

Assignment of treatment arm will be made in a 2:1 ratio stratified by study site and baseline disease severity (IGA = 3 or IGA = 4). Kits containing tubes of investigational product will be assigned to each subject by the IRT system. A subject may receive more than one kit for the treatment period. The kits and tubes will be labeled with a unique number, in a blinded manner.

### **3.6. Blinding and Unblinding**

This is a double-blind study, therefore neither the subjects nor the Investigator, clinical personnel, or sponsor will be aware of which treatment an individual receives. In the event of a medical emergency where breaking the blind is required to provide medical care to the subject, the Investigator may obtain the treatment assignment directly from the IRT system for that subject. Refer to the current version of the IRT plan for details on unblinding. Treatment assignments should, however, remain blinded unless assignment knowledge is necessary to determine subject emergency medical care. The rationale for unblinding must be clearly explained in source documentation and on the CRF, along with the date on which the treatment assignment was obtained. The Investigator is requested to contact the Sponsor promptly in the event of any treatment unblinding.

Blinding of study treatment is critical to the integrity of this clinical trial and therefore, if a subject's treatment assignment is disclosed to the Investigator, the subject will have the study treatment discontinued. All subjects will be followed until study completion unless consent to do so is specifically withdrawn by the subject.

### **3.7. Schedule of Events**

A detailed schedule of events for the study is provided in [Table 1](#).

**Table 1: Schedule of Events**

Study Procedure	Screen	Baseline Day 0	Week 2 Day 14	Week 4 Day 28	Week 8 a Day 56
Visit	1	2	3	4	5
Visit Window	-4 weeks		± 3 days	± 5 days	± 5 days
Informed consent/assent	X				
Medical/surgical history, demography	X				
Physical examination b	X	X			X
Fitzpatrick Skin Type	X				

I/E criteria	X	X			
Randomization		X			
Hematology, Chemistry, and Urinalysis c	X	X		X	X
Vital signs, weight, height d	X	X	X	X	X
IGA, Overall Assessment of Erythema, Overall Assessment of Scaling e	X	X	X	X	X
BSA f	X	X	X	X	X
DLQI/CDLQI g , Scalpdex	X	X	X	X	X
Daily WI-NRS h at home (non-clinic)			Day -7 through Day 56		
Local Tolerability Assessment i		X		X	X
Pigmentation Assessment j	X	X	X	X	X
C-SSRS, CDI-2/PHQ-8/PHQ-A k	X	X		X	X
Medical Photography l		X	X	X	X
Serum pregnancy test m	X				
Urine pregnancy test n		X		X	X
PK sampling o				X	X
IP application and subject/family training p		X	X		
Dispense investigational product kit q		X	X	X	
Dispense / review dosing diary		X	X	X	X
Weigh investigational product r		X	X	X	X
Compliance calculation s			X	X	X
Adverse event assessment t		X	X	X	X
Prior & Concomitant medications	X	X	X	X	X

***Footnotes from table above:***

- a Subjects that terminate early should return to the study site for the Week 8 assessments.
- b Limited physical examination: skin (including assessment of Fitzpatrick Skin Type at Screening only), lungs, and heart only.
- c To be collected at Screening, Baseline/Day 0, Week 4/Day 28, and Week 8/Day 56. For subjects <18 years of age, if the Baseline/Day 0 visit occurs within 3 weeks of Screening, the Screening lab results may be utilized.
- d Height will be collected at Baseline and Week 8. Weight will be collected at all study visits. Subject to void prior to weight.
- e IGA will be a 5-point scale ranging from clear (0) to severe (4). **IGA should be completed prior to other physician assessments and by the same Evaluator at each study visit.** Overall Assessment of Erythema (0-3 scale) and Overall Assessment of Scaling (0-3 scale) will be completed.
- f Total BSA affected by seborrheic dermatitis will be determined by the subject's hand method, where the subject's hand (including fingers) surface area is assumed to equal 1% of body surface area.
- g The DLQI will be completed by subjects  $\geq$ 17 years of age. The CDLQI will be completed for subjects 9 to 16 years old, inclusive.
- h WI-NRS will be completed by subjects daily at home starting 7 days prior to the Baseline/Day 0 visit to Day 56 (Week 8) visit. Daily WI-NRS will be completed in the evening prior to IP application (except at Baseline and Week 2 when IP is applied at the clinic).
- i Local tolerability assessments to be recorded prior to IP application for the Investigator assessment of skin irritation (Berger and Bowman skin irritation score) and 10-15 minutes post IP application for the subject's '0- 3' burning/stinging assessment. Note for investigator tolerability assessments: reactions at the site of IP application, which may occur post-Baseline, should be differentiated from the preexisting inflammation associated with the subject's seborrheic dermatitis. At Week 4 and Week 8, subjects will provide a recall assessment of burning/stinging experienced post IP application on the day prior to the clinic visit.
- j An assessment for hypopigmentation and hyperpigmentation will be performed by the Investigator at all clinic visits.
- k Adolescents and adults will complete the C-SSRS (12 years of age and older). Adults will complete the PHQ-8. Adolescents (ages 12 to 17 inclusive) will complete the PHQ-A (PHQ-9 modified). Parents/caregivers will complete CDI-2 (parent report) for children 9-11 years of age, inclusive. The CDI-2 will be completed throughout the study for subjects 9-11 years old at the time of assent.
- l Medical photography will be obtained for target lesions. All efforts will be made to de-identify the subjects. Subjects unwilling to participate in the medical photography will be allowed to opt out of this procedure.
- m A serum pregnancy test will be administered to all females of child-bearing potential at the Screening visit only.
- n A urine pregnancy test will be performed at the Baseline, Weeks 2, 4, and 8 to all females of child-bearing potential. A negative result is required for continued participation in the study, and results must be available at each visit prior to dispensing of investigational product.
- o PK samples (trough) will be collected on Day 28 (Week 4), and Day 56 (Week 8). Ensure investigational product is not applied in the area where PK will be drawn.
- p Subjects to apply assigned IP in the study site at every designated visit.
- q Kits will be dispensed based on % BSA. See IP Handling Plan for details.
- r Each IP canister in the Kit should be weighed and recorded at every visit. See IP Handling Plan for details.

- s Compliance calculation is described in the IP Handling Plan.
- t All AEs should be collected starting after the first application of the IP through the end of the study. All SAEs should be collected starting after the signing of the informed consent through 30 days after the last day of the IP application or the end of the study (whichever is later).

## **4. STATISTICAL ANALYSIS AND REPORTING**

### **4.1. Introduction**

Data processing, tabulation of descriptive statistics, calculation of inferential statistics, and graphical representations primarily use SAS (release 9.4 or higher). If the use of other software is warranted, the final statistical methodology report will detail what software was used for what purposes.

Continuous (quantitative) variable summaries will include the number of subjects (n) with non-missing values, mean, standard deviation (SD), median, Q1, Q3, minimum, and maximum.

Categorical (qualitative) variable summaries will include the frequency and percentage of subjects who are in the particular category or each possible value. In general, the denominator for the percentage calculation will be based upon the total number of subjects in the study population for each treatment group unless otherwise specified.

The minimum and maximum will be reported with the same degree of precision (ie, the same number of decimal places) as the observed data. Measures of location (mean and median) will be reported to 1 degree of precision more than the observed data and measures of spread (SD) will be reported to 2 degrees of precision more than the observed data.

Percentages will be presented to 1 decimal place, unless otherwise specified.

Unless otherwise indicated in section 6.1.3, all statistical tests will be conducted at the 0.01 significance level using 2-tailed tests, and p-values will be reported. Corresponding 95% and 99% confidence intervals (CIs) will be presented for statistical tests.

ARQ-154 0.3% foam will be described as “Roflumilast foam 0.3%” throughout the tables, figures, and listings.

### **4.2. Interim Analysis and Data Monitoring**

No interim analyses are planned.

## **5. ANALYSIS POPULATIONS**

The following analysis populations are planned for this study:

- **Intent-To-Treat Population (ITT):** The ITT population includes all randomized subjects. This population will be used as primary analysis population of efficacy endpoints along with disposition.
- **Per-protocol Population (PP):** The PP population will be a subset of the subjects in the ITT population, who are at least 80% compliant with study medication application, have IGA assessment at week 8, and show no “important deviations” from the study protocol that would affect the interpretation of efficacy. “Important deviations” will result from a blinded review at the end of the study and the team will determine the important deviations that can impact on efficacy.
- **Modified Intent-to-Treat Population (mITT):** The mITT population includes all randomized subjects with the exception of subjects who missed the week 8 IGA assessment specifically due to COVID-19 disruption. This population will be used for sensitivity of the primary endpoint.
- **Pruritus Population in ITT (PRU4-ITT):** This PRU population is a subset of the ITT population and includes subjects with average weekly WI-NRS pruritus score  $\geq 4$  at Baseline. This population will be used for the analysis of achievement of at least 4-point improvement in average weekly WI-NRS pruritus score as compared to Baseline.
- **Safety Population (SAF):** The Safety Population includes all subjects who are randomized and receive at least one confirmed dose of investigational product (IP). This population will be used for all safety analyses.
- **Pharmacokinetic Population (PK):** The PK population will include all subjects who received at least one confirmed dose of investigational product (IP) and provided at least one PK sample. This population will be used for summary of PK concentration results.

## 6. GENERAL ISSUES FOR STATISTICAL ANALYSIS

### 6.1. Statistical Definitions and Algorithms

#### 6.1.1. Baseline

Baseline is defined as Study Day 1. In general, the last observation recorded before the first dose of study drug will be used as the baseline for all calculations of change from baseline. For assessments where time was recorded, the last observation recorded before the first application of study drug will be used as the baseline observation for all calculations of change from baseline. If the last non-missing assessment is performed on the same date as the first study treatment administration and time is not available, it is assumed that the assessment took place prior to IP application, per study site training, and the assessment will be considered as baseline, except for adverse events (AEs) and medications starting on the first study treatment dose

administration date which will be considered post baseline.

Average weekly baseline WI-NRS is defined as the average of all non-missing scores reported during the last 7 days prior to treatment if at least 4 of 7 evaluable daily WI-NRS questionnaires are available. Daily baseline WI-NRS is defined as the last non-missing assessment prior to the first study treatment.

For subject tolerability assessments, baseline is derived as the last non-missing measurement taken on the day of first application of study drug.

### **6.1.2. Adjustments for Covariates**

Covariates for this study include pooled site group (see [Section 6.1.6](#)) and IGA severity at baseline (moderate, or severe). Subgroup analyses may be generated for the baseline covariates.

### **6.1.3. Multiple Comparisons**

Secondary endpoints will only be tested if the primary endpoint is considered statistically significant at the  $\alpha=0.01$  level. To control for multiple comparisons among the secondary endpoints, the following multiplicity procedure will be used:

[figure not shown]
Upon demonstration of statistical significance of the primary endpoint, the alpha level of 0.01 will be unequally split between two families of testing – one family for the WI-NRS success endpoints and another family for the other secondary efficacy endpoints. The testing over the WI-NRS success endpoints and the other secondary efficacy endpoints will be sequential, utilizing the Fallback Method for unused alpha.

For the testing of WI-NRS success endpoints, an alpha level of 0.0033 will be used and will use a hierarchical method to first test WI-NRS success at Week 8, followed by WI-NRS at Week 4, followed by WI-NRS success at Week 2. Should all three of these endpoints be statistically significant at the 0.0033 level, then this unused alpha will be carried to the other secondary endpoint family, which would then be tested at the  $.0033+.0067=0.01$  level. If any of the WI-NRS family do not reach statistical significance, the testing stop at that point in the WI-NRS family, but will continue in the other family, at the 0.0067 level.

In the other secondary endpoint family, an alpha level of 0.0067 (the remainder of the allotted 0.01) or the full 0.01, pending the results of the WI-NRS endpoint testing, will be used to hierarchically test: 1) IGA Success at Week 4, 2) Scaling score of 0 at Week 8, 3) Erythema score of 0 at Week 8, 4) the percentage of subjects who attain IGA of 0 at Week 8, and lastly, 5) IGA Success at Week 2.

This is illustrated in [Figure 1](#).

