#### **6.3.2. Secondary Endpoint**

Continuous secondary endpoints will be analyzed using Analysis of Covariance with treatment and stratification factors as independent variables. The ITT population will be used and missing data will be imputed using multiple imputation. Binary secondary endpoints will be analyzed similarly to the primary endpoint.

Secondary endpoints will only be tested statistically if the primary endpoint is considered statistically significant. To control for multiple comparisons among the secondary endpoints, the following multiplicity procedure will be used.

Upon demonstration of statistical significance of the primary endpoint, the alpha level of 0.01 will be unequally split between testing of the WI-NRS success endpoints and the other secondary efficacy endpoints. The testing over the WI-NRS success endpoints and the other secondary efficacy endpoints will be sequential, utilizing the Fallback Method for unused alpha.

For the testing of WI-NRS success endpoints, an alpha level of 0.0033 will be used and will use a hierarchical method to first test WI-NRS success at Week 8, followed by WI-NRS at Week 4, followed by WI-NRS success at Week 2. Should all three of these endpoints be statistically significant at the 0.0033 level, then this unused alpha will be carried to the other secondary endpoint group, which would then be tested at the  $.0033 + .0067 = 0.01$  level.

An alpha level of 0.0067 (the remainder of the allotted 0.01) or the full 0.01, pending the results of the WI-NRS endpoint testing, will be used to hierarchically test IGA Success at Week 4,

Scaling score of 0 at Week 8, Erythema score of 0 at Week 8, the percentage of subjects who attain IGA of 0 at Week 8, and IGA Success at Week 2.

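### The secondary testing rule passes alpha from the itch family to the other family but never back; a two-way transfer would hold the same 0.01 error rate and could only add rejections

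*SAP*

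**What the plan says.** Protocol 6.3.2 states: "For the testing of WI-NRS success endpoints, an alpha level of 0.0033 will be used". The order is Week 8, Week 4, Week 2. The remaining 0.0067 goes to IGA success at Week 4, scaling 0, erythema 0 and IGA 0 at Week 8, and IGA success at Week 2, also in fixed order. If all three itch tests succeed, the second family is tested at 0.0033 + 0.0067 = 0.01. SAP 6.1.3 repeats this and adds the failure branch: if any itch endpoints "do not reach statistical significance, the testing stop at that point in the WI-NRS family, but will continue in the other family", the other family stays at 0.0067. Neither text has a step that raises the itch level. SAP Table 6 lists itch at 0.0033. The SAP Figure 1 diagram is not reproduced in the text available, so it could not be checked.

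Itch success is analysed in PRU4-ITT, the subjects with baseline average weekly WI-NRS of at least 4. SAP section 5 says: "This population will be used for the analysis of achievement of at least 4-point improvement in average weekly WI-NRS pruritus score". The size of that subset is not given.

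The only power calculation is in SAP 3.2 and protocol 6.1.1: "This will provide at least 90% power to detect a 25% difference between treatment groups on IGA success", with 450 subjects at alpha 0.01. SAP 3.2 then says: "The number of subjects to be enrolled will also provide sufficient power for the secondary endpoints". It gives no figure.

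**The concern.** The two families are treated asymmetrically. Suppose the primary endpoint and all five other secondary endpoints succeed, and Week 8 itch gives a p-value between 0.0033 and 0.01. Every other tested hypothesis has been rejected, so the whole 0.01 could be spent on itch without raising the familywise error. Under the written rule itch still fails, and Weeks 4 and 2 are not tested.

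The itch tests have the least room for this. They use the smaller alpha, and they are the only tested endpoints confined to a subset. What is at stake is a possible missed itch claim with no gain in error control. The trial's type I error is not in question.

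**Working it through.** **1. The plan's own figure.** Inputs (SAP 3.2): 40% v 65%, 150 vehicle and 300 active, two-sided 0.01. Pooled rate = (150×0.40 + 300×0.65)/450 = 0.567. Null SE = √(0.567×0.433×(1/150+1/300)) = 0.0496. Alternative SE = √(0.40×0.60/150 + 0.65×0.35/300) = 0.0486. Power = Φ((0.25 − 2.576×0.0496)/0.0486) = 99.4%, which satisfies the stated lower bound of 90%. The odds ratio, 0.65×0.60/(0.35×0.40) = 2.79, also agrees.

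**2. Error control with a return path.** Take the first true null hypothesis in each family's order.
- True nulls in both families: neither family can pass on alpha until it has rejected its own true null. A first error therefore needs p < 0.0033 in the itch family or p < 0.0067 in the other. The chance is at most 0.0033 + 0.0067 = 0.01.
- True nulls in one family only: an error needs that family's first true null to have p < 0.01.

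The familywise error is at most 0.01 in every case. Simulation agrees: 0.010 within simulation error in every null configuration tried. With all itch nulls true and the other family always succeeding, the itch error is about 0.010 with the return and 0.003 without. The written rule leaves that difference unused.

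**3. Subset size (assumption).** Phase 2a (protocol 2.3.1; 226 subjects, 2:1) reports WI-NRS success of 64.6% v 33.3%, p=0.0006, at Week 8 and 52.8% v 22.8%, p=0.0005, at Week 2. For a pooled two-proportion test at 2:1, N = 4.5·z²·p̄(1−p̄)/d².
- Week 8: 4.5×3.432²×0.542×0.458/0.313² ≈ 134, or 59% of 226.
- Week 2: 4.5×3.481²×0.428×0.572/0.300² ≈ 148, or 66%.

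Of 450, that is roughly 270 to 295. The Phase 2a test is not described, so this is rough. As a check, the same method applied to Phase 2a IGA success at Week 2 (33.8% v 14.5%, p=0.0029) gives 213, close to the 226 randomized.

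**4. Week 8 itch power.** Same formula as step 1, vehicle rate 33.3%. The discounted effect applies the sponsor's IGA reduction (32.9 to 25 points) to itch: 31.3×25/32.9 = 23.8 points. Example at 270 subjects and alpha 0.0033: Φ((0.238 − 2.938×0.0645)/0.0619) = 78%.

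| Itch effect | 270 subjects, 0.0033 v 0.01 | 300 subjects, 0.0033 v 0.01 |
|---|---|---|
| 31.3 points (Phase 2a) | 97.9% v 99.2% | 98.9% v 99.6% |
| 23.8 points (discounted) | 78% v 88% | 84% v 91% |
| 20 points (illustrative) | 57% v 71% | 64% v 77% |

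The gap in each cell is the most that returning alpha could add, because it assumes the other family always succeeds in full.

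**5. Realistic gain.** The return happens only when all five other endpoints succeed at 0.0067. The documents give no rates for four of them, so their strength was assumed: all five noncentralities set to 3.5, or to the value implied by Phase 2a IGA success at Week 2 with 450 subjects (0.193/0.0446 = 4.33). Correlations were 0.6 within and 0.3 between families. At the discounted effect, Week 8 itch gains about 3 to 7 points across these choices and 270 to 300 subjects. At the Phase 2a effect it gains about 1 point or less.

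**The case against.** The plan names a sequential Fallback Method, which passes alpha forward only. It is valid and was documented before lock. Choosing it over a looped procedure can be called a matter of efficiency. At the only itch rates the documents report, power at 0.0033 is already about 98% to 99%, and it reaches 90% with 198 subjects (44% of 450). The gain needs five further successes whose likelihood the documents do not supply. Loosening the rule now, with results known, would favour the sponsor. All of this stands as a limit on the size of the point and on what can be done in this trial. It does not make the two rules equivalent: one never rejects less and has the same error bound.

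A reader might infer more, and the documents do not support it:
- **That the sufficient-power sentence is false.** It carries no figure. Power falls below 80% only with a smaller effect or a small subset. It is unquantified, not shown wrong.
- **That only about half the sample enters the itch tests.** An unpooled back-solve gives about 121 of 226 (54%). The same method recovers only 168 of 226 for Phase 2a IGA at Week 2, so it understates the number.
- **That itch power should be judged against all 450 subjects at 0.01.** That was never the itch analysis. The endpoint is defined only for baseline scores of at least 4, and below 4 a 4-point improvement is impossible.

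**Conclusion.** The point holds as a finding about efficiency. The text of protocol 6.3.2 and SAP 6.1.3, with Table 6, discards 0.0067 when the itch family stops and the other family succeeds in full. A two-way transfer has the same 0.01 bound and can only add rejections, so the written rule is dominated, though not in error.

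The benefit forgone for Week 8 itch is about 1 point or less at Phase 2a rates and roughly 3 to 7 points at a 23.8-point effect. This rests on an assumed subset of 270 to 300, a discount borrowed from IGA, assumed strength and correlation of the other endpoints, and a calculation that ignores strata, dropout and multiple imputation.

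**What to change.** The rule should read, in protocol 6.3.2 and SAP 6.1.3, with Figure 1 and the fixed alphas in Table 6 updated to match: *if all five endpoints of the other family are significant at 0.0067, that alpha passes to the WI-NRS family, where testing resumes at the first non-significant endpoint, in the same Week 8, Week 4, Week 2 order, at 0.01.* The existing transfer from the itch family stays.

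This costs a sentence and one line of decision logic, with no extra subjects or data. It belonged in Amendment 2 and SAP Version 2.0 (13-May-2022), before lock on 17-May-2022. After unblinding on 19-May-2022 it cannot support a confirmatory claim here. Any itch result that depends on it should be labelled post-unblinding and supportive, with the one-way rule kept as the confirmatory test. The rule can be adopted prospectively in later protocols.

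Optionally, SAP 3.2 and protocol 6.1.1 could replace the general statement on secondary power with the assumed PRU4-ITT size, the assumed itch effect and the resulting power at 0.0033.
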